3.8 INTERIM ANALYSES

An interim analysis for futility based on the number of confirmed objective responses observed in the activity population will be performed.

The study cut-off date for the interim analysis corresponds to the date on which the first 20 evaluable treated participants have had at least 2 postbaseline tumor assessments, experienced confirmed objective response, or have discontinued the study for any reason. For participants with 2 postbaseline tumor assessments and occurrence of response at the second postbaseline tumor assessment, the confirmatory assessment will also be included.

If 0 or 1 confirmed objective response is observed among the first 20 treated participants evaluable for anti-tumor activity, the enrollment will be stopped. Otherwise, the enrollment will continue with the 18 additional evaluable participants.

The study analysis will then be conducted in 2 steps.

The first step analysis will be conducted when all evaluable treated participants have had at least 2 postbaseline tumor assessments, experienced confirmed objective response, or have discontinued the study treatment for any reason. This study cut off can be up to approximately 20 weeks (16 weeks for 2 tumor assessments and 4 weeks for confirmation of response, if needed) after the last participant's first IMP administration. Of note, DCR will also be assessed at this cut-off.

The second step analysis for analysis of the secondary efficacy endpoints will be conducted approximately 4 months after the cut-off date for the primary analysis. At that time, the primary analysis for ORR and DCR will also be updated.

The final analysis will be conducted at the end of the study. Only safety analyses will be updated at this time.

For each analysis step, the analysis cut-off date will be defined as the date of the database extraction that will be performed for the analysis after the cut-off (study cut-off for the interim analysis, as well as the first and second analysis steps).

Analyses methods and conventions described in the other sections of this SAP will be applied for all analyses as applicable. The following additional rules will apply for analyses performed at interim analysis and at first analysis step:

- Participants without end of treatment visit performed at the time of the cut-off date will be considered as ongoing and exposed up to the cut-off date. Therefore:
 - Participants who did not complete treatment period nor prematurely discontinued the study intervention at cut-off date will be analyzed as "ongoing" in the disposition summary.
 - Their TE period, treatment period and concomitant medication period will end at the cut-off date.
 - Their treatment duration will be derived by considering date of cut-off as last IMP date.

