3 STATISTICAL ANALYSES

3.1 GENERAL CONSIDERATIONS

This study is not intended to explicitly test a hypothesis. For the primary and secondary efficacy endpoints, 95% CIs will be provided.

All efficacy endpoints based on radiological assessments of tumor burden (ie, ORR, DOR, PFS, and DCR) will be derived using the local radiologist's/Investigator's assessment.

In general, continuous data will be summarized using the number of observations available, mean, standard deviation, median, Q1, Q3, minimum, and maximum. Categorical and ordinal data will be summarized using the count and percentage of participants.

The baseline value is defined as the last available value before the first dose of IMP.

The study cut-off for analysis of the primary endpoint, ORR, corresponds to the date on which all evaluable treated participants have had at least 2 postbaseline tumor assessments, experienced confirmed objective response, or have discontinued the study treatment for any reason. For participants with 2 postbaseline tumor assessments and occurrence of response at the second postbaseline tumor assessment, it will also include the confirmatory assessment. This study cut-off can be up to approximately 20 weeks (16 weeks for 2 tumor assessments and 4 weeks for confirmation of response, if needed) after the last participant's first IMP administration. Of note, DCR will also be assessed at this cut-off.

The final study cut-off for analysis of the secondary efficacy endpoints, which include DOR and PFS, will be 4 months after the cut-off date for the primary analysis. At that time, the primary analysis of ORR and DCR will also be updated.

Observation period

The observation period will be divided into 4 segments:

- The **pre-treatment period** is defined as the period up to first IMP administration.
 - The **pre-screening period** is defined as the period from the pre-screening informed consent to the day before the screening informed consent.
 - The **screening period** is defined as the period from the screening informed consent up to the first IMP administration.
- The **on-treatment period** (ie, treatment-emergent period) is defined as the period from the first IMP administration to 30 days after the last IMP administration.
- The **post-treatment period** is defined as the period from the end of the on-treatment period.

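### SAP 3.8 uses two conflicting tests for who is still on treatment at the interim and first analysis step; read literally, a missing end-of-treatment visit extends exposure and the treatment-emergent period to the cut-off

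*SAP*

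**What the plan says.** SAP 3.8 introduces extra conventions with a limited scope: "The following additional rules will apply for analyses performed at interim analysis and at first analysis step". The lead sentence reads "Participants without end of treatment visit performed at the time of the cut-off date will be considered as ongoing and exposed" up to the cut-off. It makes no exception for death, withdrawal or a recorded discontinuation.

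Three sub-bullets follow, presented as consequences of that sentence:

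- The first concerns the disposition summary and uses another test. The group shown as ongoing is "Participants who did not complete treatment period nor prematurely discontinued the study intervention at cut-off date".
- The second: "Their TE period, treatment period and concomitant medication period will end at the cut-off date".
- The third: "Their treatment duration will be derived by considering date of cut-off as last IMP date".

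The SAP does not say whether 'Their' means the lead sentence's group or the first sub-bullet's. SAP 3.8 also fixes the date to be used: "the analysis cut-off date will be defined as the date of the database extraction".

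Elsewhere, SAP 3.1 defines the on-treatment (treatment-emergent) period as running "from the first IMP administration to 30 days after the last IMP administration". SAP 3.6.1 bases duration of exposure on the date of last administration, and SAP 5.3 ends the concomitant-medication period 30 days after last IMP.

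**The concern.** The EOT visit is not a reliable marker of whether treatment has stopped. Protocol 4.1 places it about 30 days after the last dose (±5 days in the Schedule of Activities), or earlier if a new anticancer therapy starts. Someone who dies, withdraws or is lost may never have one: Protocol 7.2 asks for an early discontinuation visit only where possible, and Protocol 7.3 provides for loss to follow-up. Discontinued participants will be in both datasets, because the cut-off definitions in SAP 3.8 count discontinuation (of the study at the interim, of study treatment at the first step) as one way of reaching the cut-off.

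A programmer who follows the lead sentence will extend exposure, the treatment-emergent period and the concomitant-medication period to the cut-off for these participants, even past a date of death. One who follows the first sub-bullet will not. Exposure, dose intensity, adverse events and deaths by period, and concomitant medications could all differ between the two. The rules lapse after the first step, so on the literal reading the same participants could change category at the second step with no new data.

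**Working it through.** The plan gives no figure on this point, so there is none to reproduce. The check compares the two readings and then applies the SAP's own formulas to an illustrative participant.

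**The two readings, for a participant who has stopped and has no EOT visit**

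| | 'Their' = lead sentence's group | 'Their' = first sub-bullet's group |
|---|---|---|
| Test | No EOT visit by cut-off | Neither completed nor prematurely discontinued |
| Treatment-emergent period ends | Cut-off | Earlier of last IMP + 30 days and cut-off |
| Last IMP date for duration | Cut-off | Actual last IMP |

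On the second reading a recorded discontinuation removes the problem. A death or withdrawal with no discontinuation recorded stays unclear.

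**Inputs**

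- Treatment-emergent end: last IMP + 30 days (SAP 3.1).
- Duration in weeks: (last IMP + 14 − first IMP)/7 (SAP 3.6.1). I take the treatment duration in SAP 3.8 to be this quantity.
- Actual dose intensity: cumulative dose ÷ duration. Relative dose intensity (RDI): actual ÷ planned (SAP 3.6.1). Planned is 100 mg/m² every 2 weeks, so 100/2 = 50 mg/m²/week.
- Assumed dates: full doses on days 1, 15 and 29; no EOT visit; death on day 75; cut-off on day 140. Day 140 is about the 20 weeks that SAP 3.1 gives as the maximum from the last participant's first dose to the primary cut-off.

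**Using the actual last dose date**

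- Treatment-emergent end = 29 + 30 = day 59. The death, 75 − 29 = 46 days after last dose, is post-treatment.
- Duration = (29 + 14 − 1)/7 = 42/7 = 6.0 weeks.
- Dose intensity = 300/6.0 = 50 mg/m²/week; RDI = 50/50 = 100%.

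**Using the lead sentence literally**

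- Treatment-emergent end = day 140, which is 140 − 59 = 81 days later and 140 − 75 = 65 days after death. The death becomes treatment-emergent.
- Duration = (140 + 14 − 1)/7 = 153/7 = 21.9 weeks.
- Dose intensity = 300/21.86 = 13.7 mg/m²/week; RDI = 13.7/50, about 27%.

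**How the effect depends on the gap from last dose to cut-off** (four on-time cycles, last dose day 43; actual duration 8.0 weeks, RDI 100%)

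| Gap (days) | Extra treatment-emergent days | Duration (weeks) | RDI |
|---|---|---|---|
| 20 | 0 | 10.9 | 73.7% |
| 30 | 0 | 12.3 | 65.1% |
| 35 | 5 | 13.0 | 61.5% |
| 90 | 60 | 20.9 | 38.4% |
| 140 | 110 | 28.0 | 28.6% |

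Duration and RDI are distorted at every gap shown. The treatment-emergent period changes only when the cut-off falls more than 30 days after the last dose.

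**Size in a rate.** One reclassified participant is 1/20 = 5.0 points if exactly 20 are treated at the interim, and 1/38 = 2.6 points at 38 treated.

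**The case against.** The best defence is grammatical. The nearest antecedent of 'Their' is the first sub-bullet's group, which excludes anyone who has discontinued. Protocol 7.1.1 requires every permanent discontinuation to be recorded in the eCRF, so on that reading most stopped participants keep their true last dose date. This is a fair reading, and it rules out stating as fact that everyone without an EOT visit will be analysed as exposed. It does not rescue the text: exposure up to the cut-off is stated in the lead sentence itself, the sub-bullets are offered as its consequences, and the first names only the disposition summary.

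A second defence is that these are declared additional rules for two analyses, so a departure from SAP 3.1 is intended. That works for participants truly on treatment. It does not explain why a missed visit should make a stopped participant exposed.

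Other limits stand:

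- Treatment-emergent status changes only for events more than 30 days after last dose. Protocol 8.3.1 requires full adverse event collection only until at least 30 days after it, so late events would mainly be those still followed or reported later.
- Death within 30 days of last dose is treatment-emergent either way.
- The fatal adverse event rows by context of death (SAP Table 5, footnotes c and d) count from last IMP administration, so the example death should not move there. It could move in the SAP 3.6.2 summary of deaths by study period.
- Time to first corneal event is already capped at death (SAP 3.6.2).
- Safety uses the all-treated population, which at the interim may exceed the 20 evaluable participants, so 5.0 points is a maximum.
- The rules lapse after the first step.

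**Conclusion.** The point holds as a conflict between two triggers, with an undefined 'Their', at the interim and first analysis step only. On the literal reading, affected participants have overstated duration, understated RDI and a treatment-emergent period that can run past last IMP + 30 days. In the example these are 6.0 against 21.9 weeks, 100% against about 27%, and day 59 against day 140. The dates are assumptions; the formulas are the SAP's. Each late death or event so reclassified adds at most 5.0 points with 20 treated, or 2.6 with 38.

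A reader might infer two stronger things that the documents do not support:

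- **That the continue/stop decision is affected.** It is not. The only stated interim criterion is 0 or 1 confirmed responses among the first 20 evaluable participants, and no safety measure enters it. ORR is also unaffected.
- **That everyone who misses the EOT visit is reclassified.** The documents give no rate. If 5% to 15% missed it (an assumption), that would be 1 to 3 of 20 or 2 to 6 of 38. For treatment-emergent events this is a ceiling, since each must also have an event more than 30 days after last dose and before the cut-off.

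It is worth correcting because the text as written permits wrong exposure and safety summaries and the remedy is simple.

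**What to change.** Replace the lead sentence in SAP 3.8 with: *Participants with no recorded permanent IMP discontinuation, death, study withdrawal or loss to follow-up at the cut-off date will be considered ongoing.* State that the three sub-bullets apply to these participants only.

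For all others, use the actual last IMP date for duration and dose intensity. End the treatment-emergent period at the earliest of last IMP + 30 days, death and cut-off, whether or not an EOT visit took place.

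The cost is a short SAP wording change and one derived flag. The discontinuation record it relies on is already required in the eCRF by Protocol 7.1.1, and Protocol 7.2 requires study withdrawals to be recorded there too. No design figure, ORR analysis or futility criterion changes.

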3.6.1 Extent of exposure

The dose information will be assessed by the following:

- Number of cycles started per participant.
- Duration of exposure (in weeks) is defined by (date of last administration of the IMP + 14 days date of first administration of the IMP)/7.
- Actual dose (in mg/m²). In case of dose interruption, actual dose will be the sum of the actual doses administered before and after the dose interruption.
- Cumulative dose (in mg/m²): the cumulative dose is the sum of all actual doses of tusamitamab ravtansine, given from first to last administration
- Actual dose intensity (ADI in mg/m²/week): defined as the cumulative dose divided by the duration of tusamitamab ravtansine exposure (in weeks)

- Planned dose intensity (PDI in mg/m²/week): corresponds to the planned dose at C1D1 + planned dose at subsequent cycles multiplied by the theoretical total number of doses started 1 and divided by the theoretical cycle duration expressed in weeks (ie, 2 weeks per cycle started)
- Relative dose intensity (RDI, in %):100 × ADI ([mg/m²/week])/PDI ([mg/m²/week])

The total number of cycles started, number of cycles started by participant will be summarized as a quantitative variable and by category (number [%] of participants receiving at least 1 cycle, at least 2 cycles, etc). Duration of tusamitamab ravtansine exposure, cumulative dose, ADI and RDI will be summarized quantitatively.

The following variables will be derived to describe dose modifications and dose interruptions:

• Dose reduction: The first administration (loading dose) and second administration (first 100 mg/m² infusion) will not be counted as a dose reduction. For the third and subsequent tusamitamab ravtansine administrations, dose reduction will be determined using the dose level intervals provided in Table 6, by comparing the current dose level to the previous dose level. If the current dose level is below the dose level interval of the previous dose administration, then the current dose Table 6 level is considered reduced.

Actual dose level	Dose level interval
Starting dose (100 mg/m² Q2W)	>90 mg/m²
Dose level -1 (80 mg/m² Q2W)	>72.5 mg/m² and ≤90 mg/m²
Low dose	>0 mg/m² and ≤72.5 mg/m²

Table 6 - Tusamitamab ravtansine dose reduction criteria

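### At the interim and first-step analyses, using the cut-off as the last dose date makes exposure run 14 days past the cut-off and, separately, understates relative dose intensity for ongoing participants

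*SAP*

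**What the plan says.** SAP 3.6.1 gives the exposure definitions.

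- Duration: "Duration of exposure (in weeks) is defined by (date of last administration of the IMP + 14 days", minus the date of first administration, divided by 7. The minus sign is missing from the text available to me; I read it as subtraction.
- Actual dose intensity (ADI): "defined as the cumulative dose divided by the duration of tusamitamab ravtansine exposure (in weeks").
- Planned dose intensity (PDI): the planned doses for the cycles started, divided by 2 weeks per cycle started.
- RDI: 100 × ADI/PDI.

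SAP 3.8 keeps these definitions in force: "Analyses methods and conventions described in the other sections of this SAP will be applied for all analyses as applicable". It then adds special rules for two analyses only: "The following additional rules will apply for analyses performed at interim analysis and at first analysis step". The lead-in reads "Participants without end of treatment visit performed at the time of the cut-off date will be considered as ongoing and exposed up to the cut-off". Two of the sub-bullets beneath it matter here: "Their TE period, treatment period and concomitant medication period will end at the cut-off date", and "Their treatment duration will be derived by considering date of cut-off as last IMP date".

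Treatment duration, the term in the last sub-bullet, is not defined anywhere as a quantity distinct from duration of exposure.

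**The concern.** Read together, the two sections put the cut-off date into a formula written for a real dose date. The 14 days in that formula stand for the cycle that a dose begins. No dose is given on the cut-off date, so no new cycle starts there.

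The reported duration then conflicts with SAP 3.8 itself, which ends exposure and the treatment period at the cut-off. ADI also divides the doses actually given by a period that includes days on which the next dose was not yet due.

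The special rules stop after the first step. A participant who is dosed fully and on time throughout could therefore show an RDI below 100% at the first step and 100% at the second, only because the convention changed. At stake is the accuracy of the exposure and dose-intensity tables in the interim and primary reports.

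**Working it through.** The documents state no exposure or RDI figure, so there is none to reproduce. The check applies the SAP formulas directly.

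**Inputs**
- Planned dose 100 mg/m² every 14 days (SAP 1.1).
- n = number of full doses, all given on schedule.
- d = days from last actual dose to cut-off. The documents do not give this. I assume 0 to 13 for a punctual ongoing participant, and show 28 to 35 for someone who has stopped and awaits the end-of-treatment visit, due about 30 days after the last dose (Protocol 4.1).

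**Formulas**
- PDI = [100 + 100(n − 1)]/(2n) = 50 mg/m²/week for every n. It does not depend on the cut-off.
- Ordinary rule (SAP 3.6.1): duration = 14(n − 1) + 14 = 14n days. ADI = 100n/(14n/7) = 50, so RDI = 100% for every n.
- SAP 3.8 rule: duration = 14(n − 1) + d + 14 = 14n + d days. RDI = 100 × 14n/(14n + d).

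**Worked case, n = 8, d = 7.** First dose on day 0, last dose on day 98, cut-off on day 105.
- Ordinary rule: 112/7 = 16 weeks; ADI = 800/16 = 50; RDI = 100%.
- SAP 3.8 rule: (105 + 14)/7 = 17 weeks; ADI = 800/17 = 47.06; RDI = 94.1%.
- Time from first dose to cut-off: 105/7 = 15 weeks. The reported duration runs 2.0 weeks beyond it.

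**RDI under the SAP 3.8 rule (correct value 100%)**

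| Doses n | d = 0 | d = 7 | d = 13 | Mean over d = 0-13 |
|---|---|---|---|---|
| 1 | 100% | 66.7% | 51.9% | 71.1% |
| 4 | 100% | 88.9% | 81.2% | 90.0% |
| 8 | 100% | 94.1% | 89.6% | 94.6% |
| 12 | 100% | 96.0% | 92.8% | 96.3% |

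**Separating the two causes.** At d = 0 the 14 days are still added and RDI is exactly 100%, so the addition does not cause the RDI error. The cause is the replacement of the last dose date by the cut-off. Removing only the 14 days gives RDI = 100 × 14n/(14(n − 1) + d). At n = 8 that is 112/98 = 114.3% for d = 0 and 112/105 = 106.7% for d = 7, which is wrong in the other direction.

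**Which rows apply.** At the first step, an evaluable participant still on treatment must have two postbaseline scans or a confirmed response. With scans every 8 weeks ± 7 days and confirmation at least 4 weeks later (Protocol 8.1), the earliest route is week 7 + 4 = week 11, by which time six punctual doses have been given (weeks 0, 2, 4, 6, 8, 10). At n = 6 and d = 13, RDI = 84/97 = 86.6%. The expected median treatment time of 24 weeks (SAP 1.1) corresponds to 12 cycles. Smaller n arises mainly among recent enrollees at the interim.

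**Stopped, no end-of-treatment visit yet, if covered.** At n = 8, RDI is 112/140 = 80.0% for d = 28 and 112/147 = 76.2% for d = 35.

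**The case against.** The strongest reply is that no sentence says 14 days are added to the cut-off. SAP 3.8 uses a different label from SAP 3.6.1, applies other conventions only where applicable, and says exposure runs to the cut-off, so a programmer might simply truncate there. It is true that the 14-day overrun is an inference from two sections. But no other duration is defined, and truncating inside the ADI formula pushes RDI above 100%. Neither reading gives a correct RDI.

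A second reply is that running time to the cut-off captures a dose delay in progress. That has some force. At n = 8 and d = 28, last dose plus 14 days gives 100%, time to the cut-off 88.9%, and the SAP 3.8 rule 80.0%. But the rule also lowers RDI for participants whose next dose is not yet due.

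Some stronger readings are tempting, and the documents do not support them:

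- A reader might infer that full dosing would show up as delays or reductions. SAP 3.6.1 derives delays from actual administration dates and reductions from dose levels, so those tables remain correct and would sit beside the RDI.
- A reader might infer that everyone who has stopped dosing but lacks an end-of-treatment visit is certainly treated as exposed. The lead-in suggests so, but the first sub-bullet speaks of participants who neither completed nor prematurely discontinued treatment, and *Their* in the next sub-bullets may refer only to them. The text is ambiguous.
- A reader might infer that the large errors seen after very few cycles describe the primary report. They do not fit punctual, evaluable, ongoing participants at the first step.

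**Conclusion.** The point holds for the descriptive exposure, ADI and RDI tables at the interim and first-step analyses. As written, exposure for every ongoing participant ends 14 days after the cut-off, against the section's own statement. RDI is understated whenever the last dose preceded the cut-off: on average by about 5 points at 8 cycles and 4 points at 12, more with few cycles, and not at all if a dose fell on the cut-off day. If participants who have stopped dosing are also covered, their understatement is larger.

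These sizes assume full, punctual dosing and 0 to 13 days from last dose to cut-off, evenly spread for the means. They apply to ongoing participants only, so a cohort summary would be diluted by those who have finished treatment.

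A reader might fear for the efficacy conclusions. The futility decision rests on confirmed responses, and the response rate does not use this duration. The second-step and final analyses fall outside the special rules.

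**What to change.** The rule is wrong as written and should be replaced in SAP 3.8. For ongoing participants at these two analyses:

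1. Compute ADI and RDI with the actual last IMP date on or before the cut-off, plus 14 days. This returns 100% for full punctual dosing at any n.
2. Truncate the reported duration of exposure at the cut-off. Step 1 alone does not do this, because last dose plus 14 days still passes the cut-off when d is 0 to 13.
3. Use the cut-off only to end the treatment-emergent, treatment and concomitant-medication periods.
4. State that participants with a recorded treatment discontinuation but no end-of-treatment visit use their actual last IMP date.

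The cost is a short text change and the matching programming, with no new data. One small downside is that a dose delay still in progress at the cut-off will not be reflected in RDI.
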